5.1. Primary objective

The primary objective of this study is to assess the risk of VTE among E4/DRSP users compared to users of EE/LNG, specifically:

- Deep Venous Thrombosis (DVT) of the lower extremities (ICD-10 codes: I80.1 and I80.2), and
- Pulmonary Embolism (PE; ICD-10 codes: I26.0 and I26.9)

5.2. Secondary objectives

The secondary objectives of this study are to assess the risk and compare it between E4/DRSP users and EE/LNG users (stratified by age, smoking, and BMI) for:

- All VTE, including thromboses of the renal, mesenteric, portal, cerebral and retinal veins⁷ (a sensitivity analysis will be done for the ICD-10 code I80.3),
- ATE, including acute myocardial infarction (AMI) (ICD-10 code I21.* 8) and cerebrovascular accidents (CVA) (ICD-10 code: I24.9, G45.*, I61.*, I63.1, I63.2, I63.3, I63.4, I63.5, I63.8, I63.9),

⁴ ClinicalTrials.gov identifier: NCT01009684

⁵ ClinicalTrials.gov identifier: NCT00335257

⁶ ClinicalTrials.gov identifier: NCT01650168

⁷ ICD-10 codes: I26.0, I26.9, I63.6, I67.6, I80.1, I80.2, I80.3, I80.8, I80.9, I81, I82.0, I82.2, I82.3, I82.8, I82.9, H34.8, K55.0 and N28.0

^{*} For all stars, it means including all codes within this category

Supporting document SOP PM01 - Doc PM3004.03

- Unintended pregnancy, and
- Neonatal malformations associated with foetal exposure to E4/DRSP and EE/LNG.
- Drug utilization pattern,
- Baseline risk profile for primary and secondary clinical outcomes—in particular for cardiovascular outcomes.

6. Research methods

6.1. Study design

This is a large, multinational, prospective, active surveillance study that follows two cohorts. The cohorts consist of new users (starters⁹ and restarters¹⁰) of two different groups of hormonal contraceptives: E4/DRSP and EE/LNG. The study will use a non-interference¹¹ approach to provide standardized, comprehensive, reliable information on these treatments in a routine clinical practice setting.

Study participants will be recruited via recruitment centres (health centres, pharmacies, telemedicine/online prescription services, and electronic medical records [see details in Section 6.2]) for the INAS-NEES study. An international network of COC-prescribing HCPs will recruit eligible COC-users over an estimated period of 5 years. After study entry, study participants will be followed for a maximum of 2 years for rare serious safety outcomes. Additional follow-up procedures (see Section 6.4.2) will be used to validate patient-reported events. A non-interventional approach will be used for the INAS-NEES study. Enrolment procedures should not interfere with the prescribing behaviour of the participating HCPs or with the individual needs of their patients. People prescribed a new COC are eligible to join the study provided they are prescribed a COC under investigation, sign an informed consent form (ICF), complete a baseline questionnaire, and understand the language of the ICF and questionnaires. Adolescents (below the age of 18 years) will be eligible to participate based on local legislation.

Through direct contact with the study participants at 6, 12, 18, and 24¹² months after enrolment, relevant clinical outcomes will be captured. However, because laypersons often over-report, or misclassify AEs (e.g., varicose veins as "thrombosis" or pneumonia as "pulmonary embolism"), patient-reported events of interest to the study will undergo careful validation. This will be accomplished by contacting the relevant HCPs (usually the treating physicians) and by reviewing medical documentation. Under routine medical conditions, clinical outcomes are not always

⁹ First-ever user of a COC

User who restarts hormonal contraceptive use with a COC (same COC as before or new COC) after an intake break of at least two months.

I.e., 1) all new users of E4/DRSP or EE/LNG are eligible for enrolment if they give their informed consent; and 2) recruitment of study participants should not influence the physician's prescribing, diagnostic, or therapeutic decisions.

¹² Or at the end of the study if the study ends prior to the 24-month follow-up of an individual participant.

Supporting document SOP PM01 – Doc PM3004.03

confirmed by diagnostic procedures with high specificity. Therefore, reported serious clinical outcomes will be classified as "confirmed" or "not confirmed" according to predefined algorithms. At the end of the study, this classification will be verified by blinded independent adjudication (see. *Annex 3.2*) by three medical experts (e.g., cardiologists, phlebologists, internists), who are proposed by ZEG and approved by the Safety Monitoring and Advisory Council (SMAC). They will assess the VTE and ATE cases independently from ZEG (see Section 6.4.3).

6.2. Setting

This multinational, prospective, controlled, primary data collection study will be conducted by the Berlin Center for Epidemiology and Health Research GmbH (ZEG Berlin) in Europe, the USA, and Brazil to collect high-quality, real-world data on new users of COCs. In parallel, the recruited users will also be included in an independently conducted ongoing registry.

It is estimated that more than 60% of the study data will be obtained from European Union (EU) countries, with the remaining proportion from non-EU countries. There is no literature evidence to suggest that risk factors in women who take COCs are different between EU and non-EU populations, except for sickle cell trait in women of African descent. Risk factors of VTE are well established and consistent across populations and include age, family disposition, obesity, smoking, immobilization, coagulation disorders, pregnancy, puerperium, and history of cancer. All these factors will be collected during this study and propensity score matching during analyses can correct for potential unbalanced groups, although this is not foreseen. Recruitment will be conducted in a 1:1 ratio on the national level to ensure an even distribution of cohorts on the local level.

The study will be overseen by an independent committee of experts, the SMAC, who will review the selected study data every 6 months and at the request of the Principal Investigator and the MAHs (see *Annex 3.1*).

The study will be divided into 2 phases: the recruitment phase and the follow-up phase. The recruitment phase starts when the study participant is introduced to the study by the HCP (i.e., after a prescription has already been agreed upon), the signing of an ICF, and the completion of a baseline questionnaire (baseline survey). The follow-up phase includes direct follow-up with the study participant at 6, 12, 18, and 24 months after study entry. The follow-up phase will end approximately one year after enrolment of the last study participant. However, participants who are enrolled within the last year of the recruitment phase will have their last routine follow-up at the end of the follow-up phase (instead of 24 months after study entry). Visits and follow-up contacts are calculated in calendar months and years following the baseline visit. In keeping with German national regulations, the recruitment process will be modified for Germany. The description of the relevant modified passages is displayed in *Annex 3.3*.

HCPs will act as recruiters, identifying potentially eligible study participants, facilitating the onboarding process, educating study participants regarding the study expectations, and consenting them to participate in the study. There will be limited additional involvement from the recruiting HCP. Importantly, the role of HCPs in this PASS should be to act as a recruiter and point of contact for the collection of the study participant's safety information. The primary method of data collection will be through patient-reported outcome questionnaires. Study participants will be followed up by the ZEG Berlin study team independent of the recruiting

Supporting document SOP PM01 - Doc PM3004.03

HCPs. In the case a study participant will report an outcome of interest to the study, the recruiting HCP may be re-contacted to clarify health outcomes of interest reported by the study participant.

The following recruitment centres will be used:

1. Health centres

A network of HCP recruitment centres will be established. Depending on the individual health care system, HCPs may be family practitioners, general practitioners, obstetricians, women's health doctors, midwives, nurse-practitioners, and/or physician assistants. The HCP may only invite eligible study participants to join the study after the decision to start E4/DRSP or EE/LNG is made. HCPs in Germany will be instructed to recruit only on-label users of the respective COCs. The HCP will explain the nature of the study to the study participant and if they will be interested, provide them with access to an online study portal that will guide them through the consenting and ICF completion process.

2. Pharmacies

Pharmacy networks will be used as point-of-sale recruitment centres to enhance study recruitment. This recruitment approach will be started in Germany and rolled out to other countries where technology and network infrastructure allow. In the German pharmacies, there will be a screening process to ensure only COC users are recruited who use the respective COCs on-label.

Pharmacy merchandise management systems will be programmed to alert pharmacies of a potentially eligible study participant at the point of sale. Pharmacists will be considered as recruiting HCPs.

All networked pharmacies will receive basic information about the study. Merchandise software will be programmed to provide basic information about the study at the point of HC sale. Following the sale of the HC, it is assumed that pharmacists will provide study participants with basic information about the study and direct those interested in study participation to the study-portal via a QR-code-based system.

Potential study participants entering the study-portal will be initially guided through a brief screening questionnaire to ensure that subjects meet the specified inclusion criteria. Following the successful screening, subjects will be guided through a consenting process. Subjects will be considered to have been successfully enrolled in the study on completion of the eConsent documentation.

3. Telemedicine/online prescription services

Digitalization of the healthcare system is an evolving process. Online consultations and the dispensing of prescriptions in the clear absence of personal doctor-patient contact are regulated and reimbursed in France, Germany, the United Kingdom (UK), and the USA. User acceptance and use of telemedicine and online prescription services have accelerated in light of the Covid-19 pandemic and the enforced social distancing policies it has necessitated.

Study participants will be invited by their telemedicine HCP to participate in the study and will be directed to the study-portal after receiving their prescription of a new HC. Potential study

ZEG Berlin

Estetra Study Protocol

Supporting document SOP PM01 - Doc PM3004.03

participants entering the study-portal will be initially guided through a brief screening questionnaire to ensure that subjects meet the specified inclusion criteria. Following the successful screening, subjects will be guided through a consenting process. Study participants will be considered to have been successfully enrolled in the study on completion of the eConsent documentation.

4. Electronic medical records

In the UK, data from the Egton Medical Information Systems (EMIS) health software platform will be used to identify potential study participants with a recent prescription of HCs. The EMIS health software is used by over 40% of all primary and acute care service providers in the UK, and currently contains over 1.9 million people who have consented to be contacted for clinical research. Following identification of people fulfilling the eligibility criteria, study participants will be contacted via their HCP, informed about the study, and consented to study participation using eConsent and electronic signature (eSignature, Electronic Identification, Authentication and Trust Services [eIDAS]-compliant).

The four recruitment strategies aim to contact potential study participants at the time of incident HC prescription and/or purchase. Utilizing several recruitment approaches will increase the speed with which study participants can be enrolled in the study and ensures that a representative group of incident HC users will be enrolled in the study, encompassing both study participants who are early adopters of telemedicine and electronic prescriptions, and HC users who prefer to access healthcare via face-to-face, clinic-based consultations.

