- Stillbirth (defined as foetal death with a gestational age ≥20 weeks)
- Neonatal death (defined as deaths occurring among live births during the first 28 completed days of life)
- Spontaneous/elective abortion (defined as a loss of pregnancy at a gestational age <20 weeks)
- Termination of pregnancy for foetal anomaly (TOPFA [where prenatal diagnosis was made of malformation in a live foetus and the pregnancy was then terminated])
- Preterm delivery (defined as delivery strictly before 37 completed weeks of gestation)
- Low birth weight (defined as a birth weight <2,500g)
- Small for gestational age infants

The list of variables in Table 1 are similar to the variables used in previous PASS conducted by ZEG-Berlin.

Supporting document SOP PM01 – Doc PM3004.03

Table 1: List of variables to be used in INAS-NEES

		Variable				
X - present; G - present in Germany only; U - present under 18 only; T - present, triggers additional follow up Participant Characteristics		p		Questionnaire		
		Baseline	Follow-up	Extra Follow-up		
	Screening	Did you take an oral contraceptive pill or any other hormonal contraceptive in the last 2 months?	Х			
		Before you were asked whether you want to take part in this study, you and your doctor decided on a new prescription for an oral contraceptive pill. Was the prevention of pregnancy the reason for this prescription?	G			
		Do you have (or have you ever had) a blood clot in a blood vessel of your legs (deep vein thrombosis, DVT), your lungs (pulmonary embolus, PE), or other organs?	G			
		Are you aware of having a disorder affecting your blood clotting – for instance, protein C deficiency, protein S deficiency, antithrombin-III deficiency, factor V Leiden, or antiphospholipid antibodies?	G			
		Do you need an operation or are you off your feet for a long time (e.g., hip/leg surgeries, neurological surgeries, trauma surgeries)?	G			
		Have you ever had a heart attack or a stroke?	G			
		Do you have (or have you ever had) angina pectoris (a condition that causes severe chest pain and may be a first sign of a heart attack) or transient ischaemic attack (TIA – temporary symptoms of stroke)?	G			
Participant Characteristics		Do you have severe diabetes with blood vessel damage?	G			
		Do you have very high blood pressure?	G			
		Do you have a severely increased blood lipids (cholesterol or triglycerides)?	G			
ant (Do you have a condition known as hyperhomocysteinaemia?	G			

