œ.	Thrombophilia	Date of being informed about Thrombophilia diagnosis	Х			
		Was Thrombophilia treated by physician?	Х			
		Type of Thrombophilia	X			
	Cancer	Date of being informed about Cancer diagnosis	Х			
		Type of cancer	Х			
		Was Cancer treated by physician?	Х			
		Was Cancer treated with chemotherapy?	Х			
	Diabetes	Date of being informed about Diabetes diagnosis	Х			
		Was Diabetes treated by physician?	Х			
	High Blood	Date of being informed about HBP diagnosis	Х			
	Pressure	Was HBP treated by physician?	Х			
	Other Severe	Description of Other severe disease	Х			
	Disease	Date of being informed about Other severe disease diagnosis	Х			

		Variable			
Category		X - present; G - present in Germany only; U - present under 18 only; T - present, triggers additional follow up		Questionnair	e
Par	ticipant Character	stics	Baseline	Follow-up	Extra Follow-up
		Was Other severe disease treated by physician?	Х		
Ì	Surgery	Description of surgery	Х		
		Date of surgery	Х		
	COVID-19	COVID-19 infection	Х	Х	
	Liver disease	Liver disease	Х		
	Renal disease	Severe renal disease/kidney disease	Х		THE STATE OF THE S
	Migraine	Migraines with neurological symptoms	Х		
Ì	Tobacco use	Smoking habit	Х	Х	Х
		Years of regular smoking	Х		
		Per day smoking	Х	Х	Х
		Vaping habit	Х	Х	Х
		Years of regular vaping	Х		
		Per day vaping	Х	Х	Х
Но	rmonal Contracept	ive Therapy	Baseline	Follow-up	Extra Follow-up
	Past Therapy	Any hormonal contraceptive use before study	Х		
		Total duration of all hormonal contraceptive use before study	Х		
Ŋ	Change	Change or cessation of hormonal contraceptive therapy since last contact		Х	
erak	Current Therapy	Brand name of current hormonal contraceptive	Х	Х	
Contraceptive Therapy		Indication for current hormonal contraceptive prescription Non-contraceptive indications for current hormonal	X		
cepti		contraceptive prescription Date of current therapy start	_ ^	X	
ıtra	Ctannad Thorany		V		
Co	Stopped Therapy	Brand name of most recently stopped hormonal contraceptive	Х	X	
ona	16.4.4.11.1	Date of therapy stop		X	
Hormonal	If Multiple Therapies	Brand name of previous hormonal contraceptive		X	
Ĭ	Since Last	Date of previous therapy start		X	
	Contact	Date of previous therapy stop		X	
		Treatment gap of min. 1 month when switching to previous therapy		X	
Eve	Duration of treatment gap in months ents of Interest - Diseases		Baseline	Follow-up	Extra
	Diagnoses	Newly diagnosed disease in study objective scope		X	Follow-u

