t-	New	since last contact Date of New DVT diagnosis		X	
ere	Deep Vein	Was New DVT treated by physician?		X	
r	Thrombosis Diagnosis	Exact diagnosis for New DVT	-	X	
s of	Diagnosis	Symptoms experienced of New DVT	 	X	
Events of Interest -		Body parts affected by New DVT		X	
Ev		Incidental risk factors experienced up to 6 weeks before New DVT		X	

E 190	Variable			
ategory	X - present; G - present in Germany only; U - present under 18 only; T - present, triggers additional follow up			
articipant Characteri	stics	Baseline	Follow-up	Extra Follow-u
	COVID-19 vaccination in the 6 weeks before the New DVT symptoms		Х	
	Brand name of COVID-19 vaccine		Х	
	Was New DVT treated with blood-thinners?		Х	
	Brand name of blood-thinner		Х	
	New DVT examinations		Х	
	New Genetic Thrombophilia examinations		Х	
	Result of New Genetic Thrombophilia Examination		Х	
	Type of New Genetic Thrombophilia		Х	
New	Date of New PE diagnosis		Х	
Pulmonary Embolism	Was New PE treated by physician?		Х	
Diagnosis	Exact diagnosis for New PE		Х	
40.00	Symptoms experienced of New PE		Х	
	Incidental risk factors experienced up to 6 weeks before New PE		Х	
	COVID-19 vaccination in the 6 weeks before the New PE symptoms Brand name of COVID-19 vaccine		X	
	Was New PE treated with blood-thinners?		X	
	Brand name of blood-thinner		X	
	Hospital admission for New PE		X	
	New PE examinations		X	
	SUMMORNOUS OF AN AND ANADOMORNOUS CONTROLLED TO THE SUMMORN OF THE		X	
	New Genetic Thrombophilia examinations		X	
	Result of New Genetic Thrombophilia Examination		X	
	Type of New Diagnosed Thrombophilia			
	Concurrent DVT diagnosis during New PE		X	
	Date of Concurrent DVT diagnosis		X	
	Body parts affected by Concurrent DVT		X	
New Myocardial Infarct	Date of New MI diagnosis		X	
Diagnosis	Was New MI treated by physician?		X	
	Exact diagnosis for New MI		X	
	Symptoms experienced of New MI		X	
	Did ECG/laboratory confirm New MI?		X	
	Hospital admission for New MI		X	
	Surgical intervention for New MI		Х	
	Type of surgical intervention for New MI		X	
New Stroke Diagnosis	Date of New Stroke diagnosis		Х	
	Was New Stroke treated by physician?		Х	
	Type of New Stroke		X	
	Exact diagnosis for New Stroke		Х	
	Symptoms experienced of New Stroke		Х	
	Duration of New Stroke symptoms		X	

0-1	Variable					
X - present; G - present in Germany only; U - present under 18 only; T - present, triggers additional follow up		Questionnaire				
Participant Characteristics			Follow-up	Extra Follow-up		

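### Section 6.2 says immobilisation is collected and can be balanced by propensity score, but Table 1 has no item on it for women outside Germany unless they report a new DVT or PE

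*Protocol*

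**What the plan says.** Section 6.2 says that the established VTE risk factors "include age, family disposition, obesity, smoking, immobilization, coagulation disorders, pregnancy, puerperium, and history of cancer". It continues: "All these factors will be collected during this study and propensity score matching during analyses can correct for potential unbalanced groups". Annex 3.3 carries the same two statements in its German version of Section 6.2.

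Table 1 (Section 6.3.2) lists the variables and the questionnaire in which each is asked. Three groups of entries matter here.

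- **Screening.** "Do you need an operation or are you off your feet for a long time" is coded G, which the table key defines as "G - present in Germany only". For German pharmacies, Section 6.2 says that "there will be a screening process to ensure only COC users are recruited who use the respective COCs on-label"; German prescribers are instructed to the same end. The rationale in Annex 3.3 is that women with absolute contraindications should not be included.
- **Follow-up.** "Incidental risk factors experienced up to 6 weeks before New DVT" and "Incidental risk factors experienced up to 6 weeks before New PE" stand inside the blocks on a newly diagnosed DVT and a newly diagnosed PE.
- **Baseline, all countries.** "Description of surgery" and the date of surgery are asked of everyone. So is a general item on risk-factor diseases or conditions that the woman knows she has.

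Section 6.7.1 builds the propensity score from baseline characteristics and uses it for inverse probability of treatment weighting.

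**The concern.** A propensity score can balance only what is recorded for women in both cohorts, whether or not they later have an event. If immobilisation is asked only in one country's screen and among women with an event, the control stated in Section 6.2 is not available. No statistical analysis plan can supply it afterwards, because the data will not exist.

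What is at stake is a confounder of the comparison that decides non-inferiority against a hazard ratio of 1.5. If women immobilised or facing surgery at entry were more often prescribed one pill than the other, the difference would go uncorrected outside Germany, apart from what the surgery item captures. Readers would meanwhile believe it had been handled: Section 6.9 counts availability of confounder information as a strength and does not list immobilisation as unmeasured.

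**Working it through.** **1. The Section 6.2 list against Table 1**

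| Risk factor in Section 6.2 | Baseline item asked in all countries |
|---|---|
| Age | Year of birth |
| Family disposition | DVT/PE in close relatives |
| Obesity | Height and weight |
| Smoking | Habit, amount per day, years |
| Coagulation disorders | Thrombophilia: date, type, treatment |
| Pregnancy, puerperium | Pregnancy in the last 3 months |
| History of cancer | Cancer: date, type, treatment |
| Immobilisation | None |

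The descriptions of the questionnaires in Sections 6.4, 6.4.1 and 6.4.2 add no item on immobilisation. The two case-only follow-up items do not name it either, so that it is asked even there is an inference.

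**2. Possible size of the effect**

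The protocol gives no figure for this, so there is none to reproduce. The prevalences and relative hazards below are assumptions: prevalence at entry p1 = 2% in one cohort and p0 = 1% in the other, and a relative hazard RR of 5 or 10.

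*Raised hazard throughout follow-up (upper bound for these inputs).* Bias factor = (1 + p1(RR - 1)) / (1 + p0(RR - 1)).

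- RR = 5: 1.08 / 1.04 = 1.038
- RR = 10: 1.18 / 1.09 = 1.083

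*Raised hazard for 6 weeks.* Section 6.5 plans about 150,000 woman-years from 101,000 women, so 150,000 / 101,000 = 1.49 woman-years each. Six weeks is 42 / 365.25 = 0.115 years, and the share of person-time is f = 0.115 / 1.49 = 0.077. Bias factor = (1 + p1 f (RR - 1)) / (1 + p0 f (RR - 1)).

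- RR = 5: 1.0062 / 1.0031 = 1.003
- RR = 10: 1.0139 / 1.0069 = 1.007

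*Six weeks, with the background hazard tripled in that window* (a further assumption, since Section 6.9 notes a higher VTE risk in the first months of use). The share of background events in the window becomes 3(0.077) / (3(0.077) + 0.923) = 0.20. Putting 0.20 in place of f gives 1.008 (RR = 5) and 1.018 (RR = 10).

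**3. Effect on the hazard ratio**

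| Scenario | True 1.40, bias against E4/DRSP | True 1.50, bias in favour of E4/DRSP |
|---|---|---|
| 6 weeks | 1.404 to 1.410 | 1.490 to 1.495 |
| 6 weeks, background hazard tripled | 1.41 to 1.43 | 1.47 to 1.49 |
| All follow-up | 1.45 to 1.52 | 1.39 to 1.44 |

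**The case against.** The strongest reply is that this is one over-broad sentence in a section on setting, and that little rests on it. Several parts of that reply stand.

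- Surgery with its date is asked of every woman at baseline and captures part of post-operative immobility. The general risk-factor item might capture more; Table 1 gives topics rather than answer options, so this cannot be seen. Neither is a question on immobilisation, and past surgery does not cover immobility from other causes.
- In Germany, screening out such women controls the factor by restriction in both cohorts. That is a form of control.
- Immobilisation that arises after the pill is started does not confound the baseline choice of pill. A baseline propensity score would not include it in any case.
- Section 6.7.1 does not rely on immobilisation by name, and Section 6.9 admits that residual confounding cannot be ruled out.

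A reader might be tempted to go further than the protocol allows. One might infer that the case-only items will be used as covariates, which would condition on the outcome; no such analysis is planned. One might also infer that prescribers steer immobilised women towards E4/DRSP because it is promoted as gentler on haemostasis. The protocol reports a more neutral haemostatic profile as a research finding, but says nothing of promotion or of such prescribing.

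The reply does not remove the contradiction. Section 6.2 asserts that this factor is collected and can be balanced, and the variable list does not provide for it.

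**Conclusion.** The point holds as a contradiction between Section 6.2 (with Annex 3.3) and Table 1. Outside Germany, immobilisation at entry is not recorded as such and cannot enter the propensity score; surgery is only a partial stand-in.

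The consequence for the primary result is probably small. With the assumed 2% against 1% prevalence and a 5- to 10-fold hazard, the hazard ratio shifts by about 0.3-0.7% if the raised hazard lasts 6 weeks, or about 0.8-1.8% if the background hazard is also tripled in that window. A reader might infer from the 4-8% figure that a true 1.40 could be pushed across the 1.5 margin. That requires the raised hazard to persist throughout follow-up, which is implausible for a transient state, and an imbalance for which the protocol gives no evidence. The point merits correction because the stated control is not there and the repair is cheap, not because the primary conclusion is shown to be at risk.

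**What to change.** Add one item to the baseline questionnaire in all countries on current, recent or planned immobilisation or surgery, enter it in Table 1, and include it in the propensity score of Section 6.7.1. Annex 1 shows that the questionnaires are still to be finalised, so this can be done before data collection. It need not be repeated at every follow-up.

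If the item is not added, correct the sentence in Section 6.2 and in Annex 3.3 to say that immobilisation is not collected from all women and cannot be adjusted for, and list it in Section 6.9 as an unmeasured confounder.

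The first option costs a slightly longer baseline questionnaire; the second costs a few sentences.
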